## 8.0 Efficacy Analyses

## 8.1 General Considerations

The primary and secondary efficacy endpoints will be analyzed based on the FAS. The primary and secondary efficacy endpoints as specified in Section 3.0 will be tested at significance level alpha = 0.1 (two-sided).

For all efficacy endpoints, the descriptive statistics will be provided by treatment group. The statistics include number of observations, mean, standard deviation, minimum, median, and maximum for continuous variables; and number and percentage of subjects for categorical variables.

Unless otherwise specified, categorical variables will be analyzed using Cochran-Mantel-Haenszel (CMH) test, stratified by prior bDMARD use. Continuous variables will be analyzed using Mixed-Effect Model Repeated Measure (MMRM) method.

Unless otherwise specified, any subject who is randomized based on a wrong stratum will be analyzed according to the correct stratum to which they should have been randomized.

"Baseline" refers to the last non-missing observation before the first administration of study drug or randomization if no study drug is given.

## 8.2 Handling of Missing Data

Missing data will be imputed using the following methods for the efficacy analyses:

#### **Non-Responder Imputation (NRI)**

An NRI approach will categorize any subject who has missing value for categorical variables at a specific visit as non-responder for that visit. In addition, subjects who prematurely discontinue from randomized study drug will be considered as non-responders for all subsequent visits after discontinuation.

#### As Observed (AO)

The AO analysis will not impute values for missing evaluations, and thus a subject who does not have an evaluation on a scheduled visit will be excluded from the AO analysis for that visit. Regardless of treatment switching or premature discontinuation of study drug, all observed data will be used in the analysis.

#### Mixed-Effect Model Repeated Measure (MMRM)

MMRM analysis will be conducted for repeated continuous measurements. Data collected after a subject discontinues study drug will be considered as missing. The mixed model includes the categorical fixed effects of treatment, visit and treatment-by-visit interaction, main stratification factors, and the continuous fixed covariate of baseline measurement. An unstructured variance covariance matrix will be used. The parameter estimation is based on the assumption of data being missing at random and using the method of restricted maximum likelihood (REML).

## 8.3 Primary Efficacy Endpoint and Analyses

## 8.3.1 Primary Efficacy Endpoint

The primary efficacy endpoint is change from baseline in DAS28 (CRP) at Week 12.

#### 8.3.2 Handling of Missing Data for the Primary Efficacy Endpoint

MMRM under assumption of data being missing at random will be used for primary efficacy analyses, unless otherwise specified.

## 8.3.3 Primary Efficacy Analyses

The first primary analysis is to test the superiority of ABBV-599 compared to placebo at Week 12 using MMRM (see Section 8.3.5.1). Two-sided 0.1 is to be used throughout in all efficacy analysis.

The second primary analysis is to test a pre-specified set of dose-response models among ABBV-105 dose groups and the placebo group at Week 12 using the Multiple Comparison Procedure – Modeling (MCP-Mod) method with borrowing historical placebo data (see Section 8.3.5.3).

## 8.3.4 Additional Analyses of the Primary Efficacy Endpoint

The additional analyses for the primary endpoint are

- (a) comparison of ABBV-599 to each ABBV-105 dose group;
- (b) comparison of ABBV-599 to the upadacitinib group;
- (c) comparison of each ABBV-105 group to the placebo group.

For the comparisons (a) - (c) 90% CI from MMRM of the treatment difference will be used (see Section 8.3.5.1). For comparison (b) and (c) historical data borrowing is also to be considered (see Section 8.3.5.2).

More details of the planned analyses can be found in Section 8.3.5 below.

## 8.3.5 Details for Primary Efficacy Analysis

### 8.3.5.1 Mixed-Effect Model Repeated Measure (MMRM) for Pair-Wise Comparison

In the pair-wise comparison analyses without historical data borrowing, the treatment mean will be estimated from MMRM method. One MMRM model including all treatment groups up to visit Week 12 data will be used.

MMRM analysis will be conducted for primary endpoint. Data collected after a subject discontinues study drug will be considered as missing. The mixed model includes the categorical fixed effects of treatment, visit and treatment-by-visit interaction, prior bDMARD use, and baseline DAS28 (CRP) measurement. An unstructured variance covariance matrix will be used. The parameter estimation will be based on the assumption of data being missing at random and using the method of restricted maximum likelihood (REML).

Least-square mean (SE) and 90% confidence interval (CI) at Week 12 for each treatment group will be presented together with between treatment difference of least-square means (SE), 90% CI and p-value from t-test for the difference = 0.

## 8.3.5.2 Historical Data Borrowing Analysis

Historical control data will be used in the comparison of ABBV-105 vs placebo (borrowing placebo data) and of ABBV-599 vs upadacitinib (borrowing upadacitinib data).

Meta-analysis results from the historical control data will be used as prior distribution for control group mean and a non-informative prior will be used for treatment group mean. Based on posterior means and variances for treatment and control groups, the probability of (Treatment mean – Control mean < 0) given the data i.e.,  $P(\mu_T - \mu_C < 0|Data)$  will be calculated. The details for historical data borrowing analysis is in Appendix D.

#### • ABBV-105 vs Placebo (Borrowing Placebo)

Historical data for placebo group consists of 349 subjects from three clinical trials with similar populations, similar inclusion and exclusion criteria; and they were conducted in a similar way as the current study. A meta-analysis shows that predicted mean (SD) and 95% confidence interval for mean are -0.80 (1.5) and [-1.06, -0.54].

In the ABBV-105 vs Placebo comparisons, 20 historical placebo subjects will be borrowed, which targets control of Bayesian type I error rate/False Positive Rate < 10%

and not exceeding study placebo sample size of 20. That is:  $n_h = 20$ ,  $\mu_h = -0.80$  and its

SE  $\sigma_h = 1.5/\sqrt{20} = 0.335$ . Therefore a conjugate prior distribution for placebo would be N (-0.80, 0.335). For ABBV-105, a "flat" non-informative prior probability distribution will be assumed, resulting in the posterior distribution totally based on the data. For supportive analysis, the dynamic borrowing based on observed bias may be performed as detailed in Appendix D.

### • ABBV-599 vs upadacitinib (Borrowing upadacitinib)

For the upadacitinib control group versus ABBV-599, historical data consist of 206 subjects from two upadacitinib studies (Phase 2: Study M13-550 Balance I and Phase 3: Study M13-542 Select Beyond). Active upadacitinib treatment group of 15 mg is considered. The meta-analysis results in the predicted estimated mean (SD) and 95% confidence interval are -2.32 (1.57) and [-2.54, -2.11].

For this comparison, 40 historical placebo subjects will be borrowed, which targets control of false positive rate < 10% and not exceeding the study sample size 40. That is:  $n_h = 40$ ,  $\mu_h = -2.32$ , and  $\sigma_h = 1.57/\sqrt{40} = 0.25$ . Therefore the prior distribution for upadacitinib would be  $N(-2.32, 0.25^2)$ . For ABBV-599, a "flat" non-informative prior probability distribution will be assumed, resulting in the posterior distribution totally based on the data. A dynamic borrowing based on observed bias may be performed as supportive analysis.

## 8.3.5.3 Dose-Response Modeling for ABBV-105

The dose-response relationship among ABBV-105 dose groups and the placebo group will be characterized for the primary endpoint using the Multiple Comparison Procedure - Modeling (MCP-Mod) method [Pinheiro 2006, Bretz 2005]. The response based on the primary analysis approach above will be used, and ADDPLAN DF software will be used to perform the MCP-Mod analyses. The posterior mean (SD) for placebo group (i.e., with

historical borrowing) will be used as primary analysis. The data directly from MMRM for placebo will also be analyzed as sensitivity analysis.

A set of 6 pre-specified standardized candidate dose-response models, as described in Table 1 will be utilized to examine the dose-response relationship. A statistically significant dose-response relationship will be declared if at least one model is identified by the MCP-Mod method to be statistically significant at  $\alpha = 0.1$  two-sided. The fitted dose-response curves will be presented graphically for all statistically significant models along with confidence bands. The minimum effective dose (MED) will be identified for each statistically significant model based on the pre-specified clinical meaningful target of -0.88. The weighted MED across all significant models will be calculated, with weight being inverse of model AIC.

Model	$f(d, \theta)$ d = dose, $\theta$ = Model Parameters	f  (d, θ) Standardized Model	Initial Value(s) for Parameter(s)
Linear	$E_0 + \delta d$	d	NA
Exponential	$E_0 + E_1\left[exp\left(\frac{d}{\delta}\right) - 1\right]$	$exp\left(rac{d}{\delta} ight)-1$	$\delta = 20$
Logistic	$E_0 + \frac{E_{max}}{1 + exp\left(\frac{ED_{50} - d}{\delta}\right)}$	$\frac{1}{1 + exp\left(\frac{ED_{50} - d}{\delta}\right)}$	$ED_{50}=5,\delta=10$
EMax	$E_0 + \frac{E_{max}d}{ED_{50} + d}$	$\frac{d}{ED_{50}+d}$	$ED_{50} = 5$
sigEMax	$E_0 + \frac{E_{max}d^h}{ED_{50}^h + d^h}$	$\frac{d^h}{ED_{50}{}^h + d^h}$	$ED_{50} = 5, h = 2$
Quadratic	$E_0 + \beta_1 d + \beta_2 d^2$	$d + \frac{\beta_2}{ \beta_1 } d^2$	$\delta = -0.01$

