## 2.0 Study Design and Objectives

## 2.1 Objectives and Hypotheses

The main objective of this dose-exploratory study is to evaluate the safety and efficacy of ABBV-105 and ABBV-599 (ABBV-105 plus upadacitinib) vs placebo on a background of csDMARDs for the treatment of signs and symptoms of RA at 12 weeks in bDMARD-inadequate response (bDMARD-IR) or bDMARD-intolerant subjects with moderately to severely active RA and to define optimal dose(s) for further development.

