#### Table 1. Candidate Models

Steps of MCPMod:

- 1. Choose a candidate set of *S* models as in Table 1.
- 2. Compute the optimum contrast for each model.
- 3. Use contrast test to find the significant *T* models while preserving FWER.
- 4. Use AIC criteria to find the most significant model from the significant *T* models found from Step 3.
- 5. Use the model found from Step 4 to fit observed data from the study and make inference (e.g., to find Minimum Effective Dose (MED) or the dose achieving certain amount of maximum effect), or use all significant models to make inference about the weighted target dose of interest.

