#### Figure D-2. Meta-Analysis for Historical Upadacitinib Data

In addition, upadacitinib-Phase III study data becomes available after this study design. A sensitivity analysis will be performed to include placebo data from upadacitinib-Phase III study in the meta-analysis (n = 144, mean (SD) = -1.01 (1.3)).

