#### D-3 Analysis Methods

The prior distributions discussed in Section D-2 will be combined with the observed data in the trial to obtain posterior distributions for the treatment and control groups. The probability of Treatment mean – Control mean < 0 given the observed data i.e.,  $P(\mu_T - \mu_C < 0|Data)$  will be calculated.

Let  $D = (x_1, \dots, x_n)$  be the data and  $x_i \sim N(\mu, \sigma^2)$ . Then  $\bar{x} \sim N(\mu, \frac{\sigma^2}{n})$ . If  $\sigma^2$  is a constant, we have the likelihood for the data

$$L(\mu|D) = p(D|\mu) \propto N(\bar{x}, \frac{\sigma^2}{n}).$$

The conjugate prior for  $\mu$  is supposed to be

$$p(\mu) \propto N(\mu_0, \sigma_0^2)$$

Then the posterior is given by

$$p(\mu|D) = L(\mu|D)p(\mu) \propto N(\mu_n, \sigma_n^2) \text{ where}$$
$$\mu_n = \frac{\sigma^2}{n\sigma_0^2 + \sigma^2} \mu_0 + \frac{n\sigma_0^2}{n\sigma_0^2 + \sigma^2} \bar{x} \text{ and}$$
$$\sigma_n^2 = \frac{1}{\frac{n}{\sigma^2} + \frac{1}{\sigma_0^2}} = \frac{\sigma^2 \sigma_0^2}{n\sigma_0^2 + \sigma^2}.$$

If  $P(\mu_T - \mu_C < 0|Data) > 0.95$ , the treatment group will be claimed as significantly better than the control group. This is equivalent to the hypothesis test of  $\mu_T - \mu_C = 0$  at one-sided  $\alpha = 0.05$  significant level.

Notice that  $(\mu_0, \sigma_0^2)$  are prior parameters determined from historical data borrowing and meta-analysis (see Section D-2).  $(\bar{x}, \frac{\sigma^2}{n})$  are LSMean and SE from MMRM based on data in the study. For treatment group, a "flat" non-informative prior probability distribution will be assumed, that is the posterior distribution is totally based on the observed data.

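### The weighted MED uses 1/AIC as its weight, so the result depends on an AIC scale that the SAP does not define; normalised exp(-dAIC/2) weights remove the dependence on the constant.

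*SAP*

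**What the plan says.** SAP 8.3.5.3 tests six candidate dose-response models with MCP-Mod. For each significant model it reads off the dose that reaches the -0.88 target, then combines the results: "The weighted MED across all significant models will be calculated, with weight being inverse of model AIC".

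The steps listed with Table 1 use AIC in a second way. Step 4 reads "Use AIC criteria to find the most significant model from the significant" models, and step 5 draws inference from that single model, "or use all significant models to make inference about the weighted target dose of interest".

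On the input, the same section says that "The posterior mean (SD) for placebo group", with historical borrowing, feeds the primary MCP-Mod analysis. Appendix D-3 adds that the in-study quantities "are LSMean and SE from MMRM based on data in the study". On software it says that "ADDPLAN DF software will be used to perform the MCP-Mod analyses".

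Neither document gives an AIC formula, says whether the likelihood is for patients or for the four dose means, or says which constants are kept.

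**The concern.** The absolute level of an AIC has no meaning; only differences between models fitted to the same data do. If every AIC shifts by the same constant, the evidence is unchanged but the ratio of two 1/AIC weights is not. One data set with one set of fitted curves can therefore give several weighted MEDs, each consistent with the SAP.

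Two further defects follow. When the AICs are large, 1/AIC is almost a plain average, and badly fitting models keep nearly full weight. When an AIC is near zero or negative, the weight becomes very large or negative and the result is no longer an average.

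This matters because the main objective in SAP 2.1 includes the aim "to define optimal dose(s) for further development", and the weighted MED is one of the SAP's few numerical outputs on dose.

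**Working it through.** **Design check.** Inputs from Protocol 7.6: SD 1.5, difference 0.88, one-sided 0.05, 40 per ABBV-105 arm, placebo 20 plus 20 borrowed. The non-centrality is 0.88 / (1.5 × √(1/40 + 1/40)) = 2.62, which gives 83.0% pairwise power (stated 83%). With 20 placebo patients it gives 68.2% (stated 68%). Minimum MCP-Mod power comes out at 85.0% and 69.1% (stated 85% and 70%). The documents give no AIC, weight or MED value to reproduce.

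**AIC scales.** Each mean has SE 1.5/√40 = 0.237. The placebo posterior has the same SE, because the prior counts as 20 patients. With Q the weighted residual sum of squares and p the number of mean parameters (linear 2; Emax, exponential and quadratic 3; logistic and sigEmax 4):
- Summary level, constant dropped: AIC = Q + 2p.
- Summary level, constant kept: add 4 × ln(2π × 0.05625) = -4.16.
- Patient level: about 134 with the constant dropped, about 590 in full.

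**Two models 4 AIC units apart: weight of the better one**
- 6 vs 10: 10/16 = 0.625
- 1.84 vs 5.84: 5.84/7.68 = 0.760
- 134 vs 138: 138/272 = 0.507
- 590 vs 594: 594/1184 = 0.502
- exp(-dAIC/2): 1/(1 + e^-2) = 0.88 on every scale

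If the smallest AIC is A ≥ 2 and the gap is d, the 1/AIC weight ratio is 1 + d/A ≤ 1 + d/2 ≤ exp(d/2). In that range 1/AIC is never steeper than exp(-dAIC/2).

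**Worked example.** Assumed observed means -0.77, -1.42, -1.81, -1.97 at 0, 5, 20 and 60 mg. They lie on an Emax curve with ED50 5 and Emax -1.3, whose MED is 5 × 0.88/(1.3 - 0.88) = 10.5 mg. All six models are significant.

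| Model | Q | Q + 2p | MED (mg) | 1/AIC weight, constant dropped | 1/AIC weight, constant kept | exp weight |
|---|---|---|---|---|---|---|
| Linear | 5.61 | 9.61 | 56.4 | 0.141 | 0.109 | 0.067 |
| Exponential | 6.32 | 12.32 | 59.5 | 0.110 | 0.073 | 0.017 |
| Logistic | 0.20 | 8.20 | 8.6 | 0.165 | 0.147 | 0.136 |
| Emax | 0.00 | 6.00 | 10.5 | 0.226 | 0.323 | 0.408 |
| SigEmax | 0.00 | 8.00 | 10.8 | 0.169 | 0.155 | 0.150 |
| Quadratic | 1.22 | 7.22 | 17.5 | 0.188 | 0.194 | 0.222 |
| **Weighted MED** | | | | **23.4** | **20.2** | **15.7** |

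At patient level, 1/AIC gives 26.9 mg (constant dropped) or 27.1 mg (full), close to the plain average 163.3/6 = 27.2 mg. exp(-dAIC/2) gives 15.7 mg there too. The linear and exponential models fit worst. They hold 25% of the weight under 1/AIC with the constant dropped and 8% under exp.

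**Negative weights.** With the constant kept, the lowest possible linear AIC is 4 - 4.16 = -0.16. The SAP's sensitivity meta-analysis includes a Phase 3 placebo arm with "n = 144, mean (SD) = -1.01 (1.3"). If the trial SD were 1.3, the constant would be -5.17 (three active SEs from 1.3/√40, placebo combined with the unchanged prior) and the floor -1.17. For exactly linear means (-0.80, -0.90, -1.20, -2.00), the best-fitting linear model has these weights:
- constant kept, SD 1.5: 1.50, all others negative
- constant kept, SD 1.3: -0.28
- constant dropped: 0.25
- exp(-dAIC/2): 0.43

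**Simulation.** 20,000 trials per scenario, the SAP's prior with no historical bias, SD 1.5, critical value 1.95. The MED is the first dose up to 60 mg reaching 0.88, with weights renormalised over significant models that reach it. The number after the curve name is the assumed effect at 60 mg. Table entries are median weighted MEDs in mg.

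| Truth | True MED | 1/AIC, constant dropped | 1/AIC, constant kept | 1/AIC, patient level | exp |
|---|---|---|---|---|---|
| Emax 0.88 | 60 | 23.7 | 23.0 | 25.1 | 22.1 |
| Emax 1.0 | 21.6 | 21.1 | 19.9 | 23.5 | 18.3 |
| Emax 1.2 | 10.5 | 17.8 | 15.7 | 21.6 | 12.6 |
| Emax 1.52 | 5.7 | 14.3 | 11.7 | 19.6 | 7.8 |
| SigEmax 1.2 | 8.2 | 16.5 | 14.3 | 21.0 | 11.3 |
| Linear 1.2 | 44.0 | 38.8 | 40.2 | 38.2 | 40.3 |
| Exponential 1.2 | 54.2 | 45.9 | 46.7 | 44.8 | 47.4 |

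For Emax 1.2, the share of trials with a weighted MED above 20 mg, the middle tested dose, is 41% (constant dropped), 34% (kept) or 59% (patient level). It is 30% under exp.

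**The case against.** **Accuracy.** exp(-dAIC/2) is not uniformly better. Against 1/AIC with the constant dropped, its RMSE is clearly lower in four of eleven scenarios (for example Emax 1.52: 8.6 vs 11.4), about even in three (Emax 1.2: 13.2 vs 13.8) and higher in four. At Emax 0.88, the only ABBV-105 effect that the plan assumes, it is slightly worse (38.5 vs 37.2). Effects above 0.88 are assumptions, running up to the historical contrast of -2.32 vs -0.80, that is 1.52. This stands, and no general gain in accuracy is claimed.

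**Negative weights look worse than they are.** In the linear example the weighted MED is 44.6 mg (constant kept, SD 1.5), 42.8 (kept, SD 1.3) or about 43 (dropped), against about 43.4 under exp. At SD 1.5 with the constant kept, a significant model has AIC ≤ 0 in 9% of significant trials under a linear truth and at most 1% under Emax. The weighted MED leaves the range of the model MEDs in at most 0.3%. The larger figures (49%, and 17% outside the range, for linear 1.2) need SD 1.3. This stands as a limit on size. A rule that can give the best-fitting model a negative weight is still not an average.

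**Shorthand or software.** The word inverse may be loose wording for Akaike weights, and the named software may fix the scale. Neither can be established from the documents. If the first is true, the correction only states the intent.

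**Low stakes.** Each model's MED is also reported, significant curves are plotted, and no rule ties dose choice to the weighted MED. This is true and limits the severity.

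**Conclusion.** The concern holds. As written, the weight is not a valid evidence weight, and the weighted MED cannot be reproduced from the SAP. In the worked example the unstated scale alone moves it from 20.2 to 27.1 mg, while exp(-dAIC/2) gives 15.7 mg throughout.

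The direction is not constant. In the steep concave scenarios (Emax and sigEmax at 1.2 and above) 1/AIC pulls the MED upward. For linear and exponential truths it pulls downward. For Emax at 0.88 to 1.0 the summary-level versions are not above the truth.

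exp(-dAIC/2) is exactly invariant to additive constants. Between patient-level and summary-level likelihoods it agrees only approximately (weights within about 0.002 in the examples), and it does not settle AIC versus a small-sample version.

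The simulated sizes rest on the assumed curves, parameter grids, the MED convention and no historical bias. The MCP test, its power, the type I error, the ranked testing and the -0.88 target are unaffected. All doses here are outputs of the averaging rule, and none is recommended. The point should be fixed before the analysis is run.

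**What to change.** In SAP 8.3.5.3, replace the inverse-AIC weight with: exp(-dAIC/2) divided by the sum of exp(-dAIC/2) over the significant models, where dAIC is the difference from the smallest AIC among those models. This keeps the averaging, is always positive and does not depend on the constant.

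Short clarifications to go with it:
- State the likelihood and the parameter count used for AIC.
- Say whether the weighted MED or the MED from the minimum-AIC model is the main one, since the text and steps 4 and 5 allow both.
- Report a significant model that does not reach -0.88 by 60 mg as not reached, with its weight. At Emax 0.88 this affects at least one significant model in 70% of significant trials, and in 26% no significant model reaches the target.

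The cost is one sentence and these clarifications. No extra data are needed, and the testing and its power do not change.

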#### Table 1. Candidate Models

Steps of MCPMod:

- 1. Choose a candidate set of *S* models as in Table 1.
- 2. Compute the optimum contrast for each model.
- 3. Use contrast test to find the significant *T* models while preserving FWER.
- 4. Use AIC criteria to find the most significant model from the significant *T* models found from Step 3.
- 5. Use the model found from Step 4 to fit observed data from the study and make inference (e.g., to find Minimum Effective Dose (MED) or the dose achieving certain amount of maximum effect), or use all significant models to make inference about the weighted target dose of interest.

#### 8.4 Secondary Efficacy Analyses

Continuous efficacy variables will be analyzed using MMRM method. It will be used for primary inference purpose the same way as for primary efficacy endpoint analysis.

Categorical efficacy variables will be analyzed using the CMH test controlling for stratification variables. The risk difference and 90% confidence intervals for the differences in each comparison will be constructed. NRI imputation will be used for missing data imputation. Point estimate of the response rate for each treatment group will also be summarized with a two-sided 90% confidence interval using Wilson's score method.

In addition, as observed (AO) analyses will be used as sensitivity analyses for DAS28 (CRP) and ACR20/50/70 response rates at all visits.

